#### 59 Power calculation

A sample size of 96 participants (48 in each group) was estimated, with two-sided t-testing, an  $\alpha$  of 60 61 5% and a power of 90%. The power calculation was based on the primary outcome measurement: 62 Change in glucose tolerance. The glucose tolerance was estimated by the total Area Under the 63 Curve (AUC) following a 4-hour 75-grams Oral Glucose Tolerance Test (OGTT). The expected mean total AUC for the plasma glucose excursion following a 4-hour 75-grams OGTT was 64 65 estimated as 1695 (SD 158) and 1800 (SD 158) after 16 weeks of treatment for the liraglutide and liraglutide placebo group, respectively. The difference in total AUC was based on unpublished data 66 in individuals with and without Impaired Glucose Tolerance (IGT) following a 4-hour 75-grams 67 68 OGTT at baseline from the study: "The Impact of Liraglutide on Glucose Tolerance and the Risk of Type 2 Diabetes in Women With Previous Pregnancy-induced Diabetes".(1) 69

70

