#### 85 Primary endpoint

The primary endpoint is the change in glucose tolerance following a 4-hour 75-grams OGTT from

87 week 0 to week 16. During the 4-hour 75-grams OGTT, blood was sampled at fixed time points: -

15, -10, 0, 5, 10, 15, 20, 30, 40, 50, 60, 90, 120, 150, 180, and 240 minutes. An analysis of covariance (ANCOVA) will be use to analyze change in glucose tolerance from week 0 to week 16 using mixed model analyses for the plasma glucose levels for the liraglutide and the liraglutide placebo group, respectively. In case of relevant baseline differences between the two groups, demographic, illness or treatment parameters will be included in the model as fixed effects together with the baseline value of the OGTTs as a covariate.

94

95 Secondary endpoints

96 Blood was also sampled for analyses of C-peptide, glucagon and incretin hormones in response to 97 the glucose load at the same fixed time points during the OGTT. Change in secretion of C-peptide, 98 glucagon and incretin hormones from week 0 to week 16 will also be evaluated using mixed model 99 ANCOVA analyses for the liraglutide and liraglutide placebo group, respectively. In case of 100 relevant baseline differences between the two groups, demographic, illness or treatment parameters 101 will be included in the model as fixed effects together with the baseline value of the relevant 102 variable as a covariate.

103

Most secondary endpoints were repeated every 4 weeks. Few secondary endpoints were only 104 105 repeated at week 0 and 16. For all repeated measurements a mixed model ANCOVA analyses will 106 be use to analyze mean change in continuous outcomes from week 0 to week 16 for the liraglutide and the liraglutide placebo group, respectively. In case of relevant baseline differences between the 107 108 two groups, demographic, illness or treatment parameters will be included in the model as fixed 109 effects together with the baseline value of the relevant variable as a covariate. Change in categorical 110 outcomes from week 0 to week 16 will be analyzed using mixed model logistic regression with the same fixed effects and covariates as described for the continuous outcomes. 111

For secondary endpoints without repeated measurements, missing data imputations will be madeusing Multiple Imputation of Chained Equations (MICE).

114

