For continuous outcomes without repeated measurements, outcomes will be analyzed using ANCOVA to detect differences between the liraglutide and the liraglutide placebo group. In the model baseline demographic, illness or treatment parameters will be included. Categorical outcomes without repeated measurements will be analyzed using a multiple mixed effect logistic

regression analysis model, where baseline demographic, illness or treatment parameters will be included.

- 121
- 122
- 123 Subgroup and sensitivity analyses

Subgroup and sensitivity analyses will be performed to assess the robustness of the primary analyses. These analyses will be performed using regression analysis for continuous outcomes and

126 logistic regression for categorical outcomes. The analyses will consider clinically or mechanistically

127 relevant baseline and intra-treatment variables, including:

- 128• Gender
- 129• Smoking

130• Antipsychotics (clozapine vs olanzapine; monopharmacy vs polypharmacy with other antipsychotic

- 131 medications)
- 132• Lipid profile
- 133• Liver function
- 134• Different groups of dysglycaemia:
- 135 a. HbA1c: 43 mmol/mol  $\leq$  HbA1c  $\leq$  47 mmol/mol, vs
- b. Impaired fasting glucose (IFG): Fasting plasma glucose (FPG): 6.1 mmol/l ≤ FPG ≤ 6.9
  mmol/l and HbA1c < 48 mmol/mol, vs

- c. Impaired glucose tolerance (IGT): two-hour plasma glucose after 75-g oral glucose
   tolerance test >7.8 mmol/l with a FPG < 7.0 mmol/l and HbA1c < 48 mmol/mol

- 140• IGT < 11.1 mmol/l vs IGT >11.0 mmol/l
- 141• Liraglutide treatment (1.2 mg vs 1.8 mg liraglutide)
- 142• Weight
- 143• Add-on psychotropic drugs/classes (antidepressants, anxiolytics etc. vs no add-on)
- 144• Antihypertensive treatment vs no antihypertensive treatment
- 145• Lipid lowering treatment vs no lipid lowering treatment
- 146• Changes in antipsychotic medication (> 20 % change in dose vs < 20 % change in dose vs no
- 147 changes in dose for clozapine or olanzapine, respectively)
- 148• Inhalation steroid vs no inhalation steroid
- 149• Body composition
- 150• Insulin resistance

- 151• Beta-cell function
- 152• Incretin hormones
- 153• Psychopathologic rating scales
- 154• Alcohol consumption
- 155• Length of disease
- 156• Diagnosis (schizophrenia vs schizotypal disorder vs paranoid psychosis)
- 157• Side effects
- 158• Serious adverse events
- 159
- 160

161 Summary of changes in the protocol

Protocol	Amendment	Approval from the Danish	Approval from the

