version		Health Authority	Ethics Committee
Version 1.2	First final protocol	March 15, 2013	March 27, 2013
Version 1.3	Screening for eligible	N/A. Only the Ethics	August 20, 2013
	patients in hospital	Committee had to approve the	
	records	amendment	
Version 1.4	Sub-study:	December 12, 2013	November 25, 2013
	"Cambridge". Extra		
	blood sampling for		
	proteomic fingerprinting		
Version 1.5	Expansion of	N/A. Only the Ethics	January 16, 2014
	recruitment area. Still	Committee had to approve the	
	single site study	amendment	
Version 2.0	1-year follow-up	September 17, 2014	September 3, 2014
Version 2.1	Adding second site:	January 19, 2015	January 12, 2015
	Aalborg		
Version 3.0	Modification of	June 2, 2015	May 12, 2015
	inclusion criteria:		
	Expansion of definition		
	of prediabetes.		
	Prolongation of study		
	period.		
Version 3.1	Sub-study: Examination	October 23, 2015	October 23, 2015
	of 10 healthy controls		
	for baseline comparisons		
Version 3.2	Prolongation of study	February 22, 2016	February 5, 2016
	period		

166	Original protoc	col, version 1.2			
167					
168	CLINICAL TRIAL	PROTOCOL			
169	. .				
170	Compound	VICTOZA®			
171	B				
1/2	Protocol title				
1/3					
174	Does a GLP-1 recep	otor agonist change	glucose	tolerance in antipsychotic-treated patients?	
1/5	Fully OT when the	2012 000121 21			
1/6	EudraCT number: A	2013-000121-31			
1//		11 1120 2404			
1/8	UIN-number: 011	11-1128-3404			
1/9					
101	Drotocol data/statu	11 1 2012	final (vo	arcian 2)	
101		15 11-1-2013;	iinai (ve	(151011 2)	
102		CATOR			
103	[name]				
104	Professor				
105	Department of Psy	chiatry O	Sign		
100	Department of Fsy Psychiatric Centre	Conenhagen	Jigii.		
188	University of Cone	nhagen Denmark	Date:		
189	onversity of coper	inagen, Dennark	Dute.		
190	CO-INVESTIGATOR	5			
191	[name] MD DI	MSc			
192	Head of Diabetes R	Research Division			
193	Department of Inte	ernal Medicine	Sign:		
194	Gentofte Hospital		0.0.11		
195	University of Coper	nhagen. Denmark	Date:		
196					
197	MONITORATION C	F THE STUDY ACCC	ORDING	TO GCP	
198	The GCP Unit, Univ	versity of Copenhag	en, Bispe	ebjerg Hospital, [name],
199	[name].			
200					
201	FINANCIAL SUPPO	RT			
202	The study has not y	yet received financi	al suppo	ort.	
203					
204	COLLABORATORS				
205	[name], M	D, PhD and [name], MD, PhD, Department of Psychiatry O,	

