### 469 **3.4 Randomisation and blinding**

Patients will be randomized to treatment with 1) Liraglutide 6.0 mg/mL, 3.0 mL pre-filled pen-injector
or 2) Liraglutide placebo, 3.0 mL pre-filled pen-injector. The randomization will be carried out by
drawing sealed opaque envelopes with the randomization code.

The supplier of Victoza® pens, i.e. Liraglutide 6.0 mg/mL, 3.0 mL pre-filled pen-injectors and placebo pens, i.e. Liraglutide placebo, 3.0 mL pre-filled pen-injectors (Novo Nordisk) will be responsible for labelling and blinding the Liraglutide 6.0 mg/mL, 3.0 mL pre-filled pen-injectors and Liraglutide placebo, 3.0 mL pre-filled pen-injectors before beginning of the treatment period and for generating the randomization

- 477 code. An emergency code will be kept at Gentofte Hospital and Psychiatric Centre Copenhagen if a patient
- 478 develops adverse events that demand knowledge on the treatment, the code may be broken.
- 479

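### The trial became two-site in January 2015, but the final SAP's primary model has no site term and its covariate rule does not provide for one; the cost is precision and chance imbalance, not systematic bias

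*Supplement*

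**What the plan says.** **Sites.** The summary of changes in the protocol describes version 1.5 (January 2014) as still single-site. The entry for version 2.1, approved on 12 and 19 January 2015, reads "Adding second site". Version 3.0 (May/June 2015) then widened the definition of prediabetes.

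**Timing of the SAP.** The final SAP reflects the trial after these changes. Its dysglycaemia subgroups include an HbA1c group (43-47 mmol/mol) that the version 1.2 inclusion criteria lack.

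**Models.** For the primary endpoint and the repeated secondary endpoints, if there are relevant baseline differences between the arms, "demographic, illness or treatment parameters will be included in the model as fixed effects", together with the baseline value as a covariate. For outcomes without repeated measurements the same three types enter without that condition: "In the model baseline demographic, illness or treatment parameters will be included". Missing data for those outcomes are imputed by MICE, with no predictors listed. No model names site or centre.

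**Subgroup and sensitivity analyses.** These cover "relevant baseline and intra-treatment variables, including" more than 20 named items. Site is not among them, although the list is worded as open.

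**Allocation.** Protocol version 1.2, section 3.4, randomises by "drawing sealed opaque envelopes with the randomization code" and describes no stratification by site. That text predates the second site.

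**The concern.** Site is a design factor known before any outcome is seen. Here it is also tied to calendar time, since the second site could recruit only from 2015, and some or much of its recruitment may fall under the widened entry definition. A model without site has one of two consequences, depending on how allocation was done:

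- **Allocation not organised by site.** The arms can differ by chance in their share of second-site patients. Any site difference in the analysed outcome then passes into that trial's treatment estimate and adds to its variance.
- **Allocation organised by site.** The arms are close to balanced within site, but the analysis ignores this. Between-site variance stays in the residual and the standard error is too large.

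The same term deals with both. As written, the primary rule lets covariates in only when the arms are seen to differ. Even a generous reading that counts site as an illness or treatment parameter would therefore leave its inclusion dependent on the data.

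**Working it through.** **Inputs from the SAP, Power calculation.** The plan states: "A sample size of 96 participants (48 in each group) was estimated, with two-sided t-testing", alpha 5%, power 90%. Mean total AUC is "1695 (SD 158) and 1800 (SD 158) after 16 weeks of treatment" for liraglutide and placebo. The difference is 105 and the SD 158.

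**Inputs not in the documents, assumed.** Second-site share p = 10-30%. Site difference D = 0.25-1.0 within-site SD in the analysed outcome, which is about 40-158 AUC units if that SD is 158.

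**Step 1: the plan's own figure.** n per arm = 2 × (1.960 + 1.282)² × (158/105)² = 47.6, rounded up to 48, so 96 in total. Power at 48 per arm is 0.902 by the normal approximation and 0.897 by the noncentral t. The stated size is reproduced and is not in dispute.

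**Step 2: standard error with site in the model.** Taking 158 as the within-site SD, SE = 158 × √(2/48) = 32.3 AUC units.

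**Step 3: effect of leaving site out.**

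- SE inflation factor = √(1 + p(1−p)D²)
- One-SD chance shift in the treatment estimate, allocation not organised by site = D × 158 × √(p(1−p) × 2/48)

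| p | D (SD) | SE inflation | Power at 96 | One-SD chance shift (AUC) |
|---|---|---|---|---|
| 10% | 0.25 | 0.3% | 0.901 | 2.4 |
| 10% | 0.5 | 1.1% | 0.896 | 4.8 |
| 10% | 1.0 | 4.4% | 0.877 | 9.7 |
| 20% | 0.25 | 0.5% | 0.900 | 3.2 |
| 20% | 0.5 | 2.0% | 0.891 | 6.5 |
| 20% | 1.0 | 7.7% | 0.856 | 12.9 |
| 30% | 0.25 | 0.7% | 0.899 | 3.7 |
| 30% | 0.5 | 2.6% | 0.888 | 7.4 |
| 30% | 1.0 | 10.0% | 0.841 | 14.8 |

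**Step 4: the last two effects are one thing.** Unadjusted variance = 32.25² + shift². For p = 30% and D = 1: 1040 + 218 = 1258, and its square root is 35.5 = 32.25 × 1.10. So when allocation is not organised by site, the unadjusted standard error already carries the chance imbalance.

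**Step 5: allocation organised by site, site omitted.** The true SE is about 32.3, but the reported SE is larger by the inflation factor. The actual two-sided error rate is 2 × [1 − Φ(1.96 × factor)]. This gives 0.049 at p = 10%, D = 0.25; 0.044 at p = 30%, D = 0.5; and 0.031 at p = 30%, D = 1. All are below 0.05, so the test is conservative.

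**Step 6: how likely is a visible imbalance?** The exact hypergeometric probability that the site share differs between two arms of 48 by at least 10 percentage points is 9% with 10 second-site patients, 31% with 19, 21% with 20, 37% with 29 and 27% with 30. The jumps come from odd against even counts at the cut-off. The one-SD shift in Step 3 is the steadier measure.

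**The case against.** A reader might infer that site differences bias the treatment effect. The documents do not support this. Under randomisation, site enters only through chance imbalance, which the unadjusted standard error covers (Step 4). If allocation was by site, the test errs on the safe side (Step 5). This part of the objection stands in full.

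The assumed site differences may also be too large. A difference of 1 SD is 158 units, about 1.5 times the whole planned contrast of 105, which the SAP derives from people with and without impaired glucose tolerance. The endpoint is change from week 0 to week 16, and the SAP provides for the baseline OGTT as a covariate, so stable differences in case mix or assay level are largely removed. This also stands, and 1 SD is therefore only an upper bound. What remains is a site difference in change.

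A further tempting inference is that randomisation was not stratified by site. Only version 1.2 is reproduced, and how envelopes were issued at the second site would belong to version 2.1. Silence in section 3.4 cannot be held against the plan. Nor do the documents describe different staff or OGTT handling at the second site.

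Two points stand in part. The changed entry definition is partly covered by the planned analysis by dysglycaemia group, and the open sensitivity list does not exclude a site analysis. But an unlisted analysis is not prespecified, and neither of these puts site in the primary model. A compulsory site term in every logistic model would also risk sparse cells or separation if the second site is small, so the fix is limited accordingly.

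**Conclusion.** The gap is real: the trial had two sites, and the final SAP's primary model neither contains site nor has a covariate rule that provides for it. The consequence is limited to precision and chance imbalance, with no systematic bias and no invalid test.

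For a site difference of up to 0.5 SD, the standard error rises by 0.3-2.6% and power stays at about 0.89-0.90. At 1 SD the rise is 4-10%, and power falls to 0.84 in the worst case. The one-SD chance shift runs from 2 to 15 AUC units across the whole range, against a standard error of about 32 and a planned effect of 105.

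These figures rest on an assumed second-site share of 10-30%, an assumed site difference, and 158 taken as the within-site SD of the analysed outcome. None of the three can be checked in the documents. The percentage inflations depend only on p and D; the AUC shifts also scale with the SD. Severity is low to moderate.

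**What to change.** - **Primary model and continuous secondary models:** add site (original against second site) as a fixed effect, regardless of observed balance.
- **MICE:** include site as a predictor.
- **Logistic models:** include site only where cell counts allow, and say so in advance.
- **Reporting:** show the treatment effect by site descriptively, and state whether allocation was organised by site from version 2.1.

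The cost is one degree of freedom per model and one line in the SAP. No new data should be needed, on the assumption that each participant's site is recorded; the documents do not say so expressly. Sample size and visits are unchanged.

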#### 71 Procedure

All analyses will be carried out with the treatment groups still blinded and labeled as "treatment group A" and "treatment group B". Before dividing participants into group A and group B, the statistical plan was completed and uploaded on clinicaltrials.gov, and the data set was locked. The final unblinding of treatment groups (liraglutide or liraglutide placebo), will not be carried out until all statistical analyses are performed. All analyses will be performed using SAS 9.4, with  $\alpha$  set at 0.05 and two-sided testing.

All efficacy analyses will be performed using a modified intention-to-treat principle. All participants who were randomized, received at least one dose of the trial compound (liraglutide or liraglutide placebo) and who had at least one assessment after baseline will be included in the efficacy analyses. All safety analyses will be performed in the intent-to-treat sample that includes all participants, who were randomized and received at least one dose of the trial compound (liraglutide or liraglutide placebo).

84

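### The SAP counts regressions on variables that arise during treatment as robustness evidence, and some of its subgroup classes overlap or leave values unassigned

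*Supplement*

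**What the plan says.** The final SAP, under Subgroup and sensitivity analyses, gives the purpose: "Subgroup and sensitivity analyses will be performed to assess the robustness of the primary analyses". The method is regression for continuous outcomes and logistic regression for categorical ones. The variables to be considered are "relevant baseline and intra-treatment variables, including" a list of 24 items.

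Four items can only arise after randomisation:

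- the dose item, "Liraglutide treatment (1.2 mg vs 1.8 mg liraglutide";
- the antipsychotic item, "Changes in antipsychotic medication (> 20 % change in dose vs < 20 % change in dose vs no" change;
- side effects;
- serious adverse events.

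Weight, body composition, insulin resistance, beta-cell function and incretin hormones are listed without a time point.

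The list also sets three dysglycaemia groups against each other: (a) HbA1c 43 to 47 mmol/mol; (b) fasting glucose 6.1 to 6.9 mmol/l with HbA1c below 48; (c) two-hour glucose above 7.8 mmol/l with fasting glucose below 7.0 and HbA1c below 48.

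The section does not say whether a variable enters as a stratum or a covariate, whether an interaction is fitted, or whether the results are exploratory.

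**The concern.** Randomisation protects a treatment comparison within levels of a factor fixed before treatment. It does not protect one within levels of something that treatment can change. Protocol version 1.2, section 3.5, ties a dose below 1.8 mg to adverse events. Section 4.3 requires a stable antipsychotic dose at entry, so a dose change happens on trial. If patients who tolerate the drug poorly also differ in glucose response, a contrast by dose reached or by side effects mixes that difference with any drug effect.

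The declared purpose raises the stakes. A reader would take agreement across these regressions as support for the primary result, and disagreement as doubt. Neither inference is safe. A sensitivity analysis varies an assumption of the primary analysis, such as how missing week-16 tests are handled. This section only lists variables.

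The overlapping classes are a separate and smaller fault. Where a patient can belong to two of the groups being compared, the contrast has no defined meaning.

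**Working it through.** **1. The plan's own figure.** Inputs from the SAP, Power calculation: means 1695 and 1800 (difference 105), SD 158, two-sided alpha 5%, power 90%.

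n per group = 2 × (1.960 + 1.282)² × 158² / 105² = 47.6, rounded up to 48, or 96 in total. This agrees with "A sample size of 96 participants (48 in each group) was estimated". The exact t-test power at 48 per group is 89.7%. The sample size is not in question; 105 and 158 serve below as the scale.

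**2. The listed dose contrast, 1.2 versus 1.8 mg within liraglutide, with no true dose effect.** Assumptions not in the documents: a share f = 20% stays on the lower dose, being the least tolerant on a normal scale, and tolerance correlates r with the AUC.

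- The 20% point of the normal is −0.842, where the density φ is 0.280.
- Mean tolerance of the lowest 20%: −0.280/0.20 = −1.400 SD.
- Mean tolerance of the other 80%: +0.280/0.80 = +0.350 SD.
- Gap: 1.750 SD. False AUC difference = 1.750 × r × 158.

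| r | False difference (AUC units) | Share of 105 |
|---|---|---|
| 0 | 0 | 0% |
| 0.2 | 55 | 53% |
| 0.3 | 83 | 79% |
| 0.4 | 111 | 105% |

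The sign depends on whether poor tolerance goes with a higher or a lower AUC.

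**3. Precision of that contrast.** With 48 on liraglutide and 20% on the lower dose, the split is about 10 versus 38. The standard error is 158 × √(1/10 + 1/38) = 56, so the 95% half-width is 1.96 × 56 = 110. Power for a real difference of 105 would be 46% (29% to 55% for shares of 10% to 30%).

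**4. Conditioning on side effects, with a true effect of −105 in everyone.** Assumptions: side effects in 40% of the liraglutide group and 15% of the placebo group; the prognostic factor behind them correlates r with the AUC and 1/√2 with the tendency to side effects.

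- Mean tendency among those with side effects: 0.386/0.40 = 0.966 on liraglutide, 0.233/0.15 = 1.554 on placebo. Gap: −0.588.
- Among those without: −0.386/0.60 = −0.644 and −0.233/0.85 = −0.274. Gap: −0.370.
- Multiply each gap by 158 × r/√2, which is 22.3 at r = 0.2 and 44.7 at r = 0.4, and add −105.
- With side effects: −118 to −131. Without: −113 to −122.

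Both strata are biased in the same direction while the overall effect stays at −105. The bias vanishes if r = 0. In this model it also vanishes if side effects are equally frequent in both groups.

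**5. The classes.**

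- A patient with HbA1c 45 mmol/mol, fasting glucose 6.5 mmol/l and two-hour glucose 9.0 mmol/l meets groups a, b and c at once. Protocol section 3.1.2 itself names combined IFG/IGT. The SAP gives no rule for assigning such a patient.
- A dose change of exactly 20% lies neither above nor below 20%.
- Section 3.5 allows for patients held at 0.6 mg, who fit neither dose class. Section 5.2 mentions only those held at 1.2 mg, so the two sections need to be reconciled.

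**The case against.** The strongest reply is that these are supportive analyses. The primary model, its type I error and the 96 participants do not depend on them, and the SAP says only that the regressions will consider the variables. That stands, and it limits the severity. It does not rescue the section, because the SAP gives these analyses a robustness role and conditioning on a post-randomisation variable is open to bias whether it enters as a stratum or a covariate.

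A reader might infer more than the documents support:

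- *That the dose split breaks the blind*, since the SAP, Procedure, says "The final unblinding of treatment groups (liraglutide or liraglutide placebo), will not be carried out until all statistical analyses are performed". Protocol section 5.2 steps placebo through the same nominal doses, so dose reached can be tabulated within groups A and B. For the same reason it is too strong to say that low-dose patients have no placebo counterpart. The counterpart would, however, be selected by a different tolerance.
- *That overlap makes the dysglycaemia comparisons non-randomised.* If the groups are defined at baseline, liraglutide versus placebo within each is still randomised. Only the contrast between groups is undefined.
- *That "IGT < 11.1 mmol/l vs IGT >11.0 mmol/l" overlaps.* At one decimal, the precision that protocol section 4.3 uses, it is a clean split. Likewise, the middle antipsychotic class plainly means some change below 20%.
- *That patients with more than a 20% antipsychotic change are mainly early leavers.* Protocol section 4.5 lists such a change only as a possible reason for withdrawal and encourages final evaluations. Later protocol versions are not shown.
- *That 24 separate tests give a 71% chance of a false positive* (1 − 0.95²⁴). This needs independence and one test per item. The SAP states neither, and several items are probably related. It is silent on interactions; it does not exclude them.

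**Conclusion.** The concern holds and should be fixed; the primary result does not depend on it. The SAP assigns a robustness role to regressions on dose reached, side effects, serious adverse events and antipsychotic dose change. The same applies to weight, body composition, insulin resistance, beta-cell function and incretin hormones unless their week-0 values are used.

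The size of any bias cannot be derived from the documents. Under the stated assumptions, a false dose-group difference would be about half to all of the planned effect, and it disappears if tolerance is unrelated to outcome. These figures show that the bias could matter, not that it will occur.

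The class faults are definitional: dysglycaemia groups that overlap, and two cases with no class.

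**What to change.** Changes to the SAP:

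1. Restrict subgroup analyses to values measured at week 0, and state this for every item on the list.
2. Test each factor by a treatment-by-factor interaction in the primary model, and label these analyses exploratory.
3. Report dose reached, side effects, serious adverse events and antipsychotic dose change descriptively, without p-values, and do not call them robustness checks.
4. Define exclusive and exhaustive dysglycaemia cells, for example: IGT with or without IFG; IFG without IGT; raised HbA1c only. The patient in the worked example then falls in the first cell alone.
5. Assign a change of exactly 20%, and patients held at 0.6 mg, to a class in the descriptive tables.

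The cost is SAP wording and fewer analyses. Some hypothesis-generating tests on post-treatment variables are lost, but the same data remain available as descriptions.
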